#### *11.4.3.1.2 Death*

The following summaries will be generated depending on the overall incidence:

- Number (%) of patients who died by study period (TEAE, on-study) and reasons for death summarized on the safety population
- Death in nonrandomized patients or randomized and not treated patients
- Treatment-emergent adverse events (TEAE) leading to death (death as an outcome on the AE CRF/eCRF page as reported by the Investigator) by primary SOC, HLT, HLT, and PT showing number (%) of patients sorted by internationally agreed order of SOC and alphabetic order of HLT, HLT, and PT.

Patient data listings will be provided for all TEAEs, treatment-emergent SAEs, AEs leading to treatment discontinuation, AESIs, and deaths.

#### **11.4.3.1.3 Clinical laboratory evaluation, vital signs, and electrocardiogram data**

Results and change from baseline for the parameters will be summarized by treatment group for baseline and each post baseline time point, endpoint, minimum, and maximum value. Summary statistics will include number of patients, mean, SD, median, Q1, Q3, minimum, and maximum.

The proportion of patients who had at least 1 incidence of PCSA at any time during the treatment emergent period will be summarized by treatment group. Shift tables showing changes with respect to the baseline status will be provided.

Listings will be provided with flags indicating clinically out-of range values, as well as PCSA values.

### **11.4.4 Pharmacokinetics, pharmacodynamics, and analyses of antidrug antibodies**

#### **11.4.4.1 Pharmacokinetic analysis**

Serum concentrations of functional SAR440340 and dupilumab will be summarized using arithmetic and geometric means, SD, standard error of the mean (SEM), coefficient of variation (CV%), minimum, median, and maximum by treatment per visit.

#### **11.4.4.2 Anti-drug antibodies analysis**

The ADA analysis will be detailed in the SAP.

#### **11.4.4.3 Pharmacodynamics**

The values to be used as baseline will be those collected on Day 1 (predose assessments). If any of the scheduled assessments on Day 1 are technically disqualified (eg, insufficient sample) and the parameters are measured at any of the screening visits, then values determined at screening can be used as the baseline.

For all parameters, raw data, absolute changes from baseline and percent changes from baseline will be summarized by treatment group and time point using descriptive statistics.

Summary plots (mean±standard error of the mean) on raw data, absolute changes from baseline, and percent changes from baseline will be provided by treatment group.

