### 5.3 OTHER OBJECTIVES

- Evaluation of the calibrator (dupilumab) arm performance.
- To evaluate the effects of SAR440340 and the coadministration of both compared to placebo on:
  - Other spirometric assessments (peak expiratory flow [PEF], forced vital capacity [FVC], forced expiratory flow [FEF] 25-75%).
  - Patient reported outcomes.
  - Immunogenicity (ie, anti-drug antibodies [ADA]).
  - The PK profile of SAR440340 and dupilumab in serum.
  - Selected biomarkers of the IL33 and IL4/IL13 pathway.
- Furthermore, the effects of the coadministration of SAR440340 and dupilumab on relevant endpoints compared to each monotherapy treatment arm will be assessed as well.

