2.4.4 Analyses of efficacy endpoints

All efficacy endpoints will be analyzed using the mITT population. [Table 4](#) summarizes the pairwise comparisons to be conducted in accordance with study objectives. Each comparison on each endpoint will be tested at a two-sided 5% significance level.

Table 4 - Pairwise comparisons and study objectives

	Primary endpoint	Secondary endpoints	Other efficacy endpoints
SAR440340 vs. placebo	P	S	O
Coadministration of SAR440340 and dupilumab vs. placebo	P	S	O
Coadministration of SAR440340 and dupilumab vs. SAR440340	O	S	O
Coadministration of SAR440340 and dupilumab vs. dupilumab	O	S	O
Dupilumab vs. placebo (as calibrator only)	O	O	O

P: Primary objective; S: Secondary objective; O: Other objective

2.4.4.1 Analysis of primary efficacy endpoint(s)**Main statistical model and adjustment of covariates**

The primary endpoint of incidence of LOAC will be analyzed using a logistic regression model. The model will include terms for treatment, baseline eosinophil strata, region (pooled countries), background ICS dose level at randomization and number of exacerbation events within 1 year prior to screening.

For each pairwise treatment comparison, the odds ratio, and corresponding 95% confidence interval (CI) and two-sided p-value will be derived from this model. Sample SAS code is provided below:

```
proc genmod data=loacdata descending;
  class trt01pn eosbgp1n cntygr1 icsgrp;
  model resp = trt01pn eosbgp1n cntygr1 icsgrp asmanum /dist=bin
link=logit type3;
  estimate "SAR440340 vs Placebo"      trt01pn -1 1 0 0 / exp;
  estimate "Coadministration vs Placebo" trt01pn -1 0 1 0 / exp;
  estimate "Coadministration vs SAR440340" trt01pn 0 -1 1 0 / exp;
  estimate "Coadministration vs Dupilumab" trt01pn 0 0 1 -1 / exp;
  estimate "Dupilumab vs Placebo"        trt01pn -1 0 0 1 / exp;
  ods output Estimates = Estimates;
run;
```

All reported LOAC events will undergo the standard medical review process to ensure the events are in-line with the protocol definition. For patients discontinued due to a reason other than LOAC, but for which LOAC could be suspected, the case will be medically reviewed, with appropriate queries sent to the respective site, for final determination of LOAC status to be recorded in the clinical database prior to database lock. As such, there should not be missing data for the primary LOAC endpoint.

Supportive analysis

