2.4.4.2 Analyses of secondary efficacy endpoints

Main statistical model and adjustment of covariates

Change from baseline in pre- and post-BD FEV1 at Week 12 will be analyzed using a mixed-effect model with repeated measures (MMRM) approach. The analysis model will include change from baseline values up to week 12 as response variable and treatment, gender, baseline height, baseline eosinophil strata, region (pooled countries), background ICS dose level at randomization, visit, treatment-by-visit interaction, baseline value and baseline-by-visit interaction as covariates.

Given the potential effects on FEV1 and the goal to obtain as precise a treatment effect estimate as possible, FEV1 values after a LOAC event or initiation of rescue medication will not be included for primary assessment of the secondary endpoints. Inclusion of change from baseline in FEV1 values in the model will follow the rules in Table 5. Data not included in the analysis according to these rules will be set to missing. No imputation will be made for other missing FEV1 measurements.

Table 5 – Data inclusion rules for analyses of secondary and other efficacy endpoints

If the patient has	Use data up to
LOAC with rescue medication ^a	last value before start of LOAC
LOAC without rescue medication ^b	value collected at EOT
OCS use without LOAC	last value before start of OCS
neither LOAC or OCS	value collected at Week 12/EOT

^a If the patient meets at least one of the following three criteria:
- ≥6 additional reliever puffs of salbutamol/albuterol or levosalbutamol/levalbuterol in a 24 hour period (compared to baseline) on 2 consecutive days
- Increase in ICS ≥4 times the last prescribed ICS dose (or ≥50% of the prescribed ICS dose at V2 if background therapy withdrawal completed)
- Requiring use of systemic (oral and/or parenteral) steroid treatment

^b If the patient meets none of the three criteria listed above and meets one or both of the following:
- A 30% or greater reduction from baseline in morning PEF on 2 consecutive days
- Requiring Hospitalization or emergency room visit

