2.4.4.4 Additional efficacy analysis(es)

2.4.4.4.1. Change from baseline analysis in other continuous endpoints

Change from baseline in AM/PM PEF, FVC, FEF 25%-75%, ACQ-5 score, AQLQ(S) domain scores, AQLQ(S) overall score, RQLQ(S) domain scores, RQLQ(S) overall score, AM/PM asthma symptom score, number of nocturnal awakenings, and number of inhalations/day of albuterol or levalbuterol for symptom relief will be analyzed using the MMRM approach described above. Inclusion of data will follow the rules listed in [Table 5](#). The covariates will be treatment, baseline eosinophil strata, region, background ICS dose level at randomization, visit, treatment-by-visit interaction, baseline value and baseline-by-visit interaction. Gender and height will also be included in the model for spirometry endpoints. No imputation will be performed on missing values.

Descriptive statistics including number of patients, mean, standard error, and LS means will be provided for each treatment group. Difference in LS means and the corresponding 95% CI and p-value will be provided for each pairwise treatment comparison.

A responder analysis will also be performed for ACQ-5 and AQLQ(S) endpoints, where responder status is determined based only on data included according to the rules in [Table 5](#). A logistic regression model will be used to compare the percentage of patients reaching the MCID (responders) at Weeks 4, 8, and 12 for ACQ-5 and AQLQ(S) overall scores. For ACQ-5, a patient is considered as a responder if change from baseline in ACQ-5 is ≤ -0.5 , or as a non-responder if change from baseline is > 0.5 or missing. For AQLQ(S), a patient is considered as a responder if change from baseline in AQLQ(S) global score is ≥ 0.5 , or as a non-responder if change from baseline is < 0.5 or missing.

At each time point, the model will include treatment, baseline score, baseline eosinophil strata, region and background ICS dose level at randomization. Odds ratio, the corresponding 95% CI and p-value will be derived for each pairwise treatment comparison. Descriptive statistics including number and percentage of responders will also be provided.

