2.4.6.2 Pharmacodynamics/genomics analyses

PD biomarkers will be analyzed in the safety population. Baseline values will be the last value collected prior to the first IMP.

For all parameters, absolute change from baseline and percent change from baseline will be summarized descriptively (number, arithmetic and geometric means, SD, SEM, CV, median, minimum, and maximum) by treatment group and time point. Values reported as below the LLOQ will be imputed as LLOQ/2.

Summary plots (mean +/- standard error of the mean) of levels, absolute changes from baseline and percent changes from baseline by visit and plot of median percent change (with interquartile range) from baseline by visit will be provided for each biomarker by treatment group.

Exploratory analysis of DNA/RNA will be addressed in a separate document.

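### The biomarker objective is a comparison with placebo, but both documents prespecify only by-arm descriptive summaries, with no between-arm estimate and no rule for post-LOAC samples at Week 12

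*Protocol*

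**What the plan says.** The list in Protocol 5.3 opens "To evaluate the effects of SAR440340 and the coadministration of both compared to placebo on", and one of its items is "Selected biomarkers of the IL33 and IL4/IL13 pathway". The section then adds that coadministration will be compared with each monotherapy on relevant endpoints.

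For the analysis, Protocol 11.4.4.3 states that "raw data, absolute changes from baseline and percent changes from baseline will be summarized by treatment group and time point using descriptive statistics". SAP 2.4.6.2 keeps to this: "PD biomarkers will be analyzed in the safety population", and "absolute change from baseline and percent change from baseline will be summarized descriptively" by treatment group and time point, with plots.

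The comparative parts of the SAP do not reach the biomarkers:

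- Table 4 in SAP 2.4.4 "summarizes the pairwise comparisons to be conducted in accordance with study objectives", but its columns cover only primary, secondary and other efficacy endpoints.
- SAP 2.4.4.4.1 names the variables that "will be analyzed using the MMRM approach described above". No biomarker is among them.
- Table 5 in SAP 2.4.4.2 is titled "Data inclusion rules for analyses of secondary and other efficacy endpoints". The biomarkers belong to neither class.

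**The concern.** The objective is an effect relative to placebo, and the planned output is a set of within-arm summaries. In an add-on trial with stable background therapy that gap might be harmless. Here the background therapy is removed in every arm during treatment, so change from baseline late in the trial is not a drug effect in any arm.

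The Week 12 column is also open to differential handling. LOAC stops IMP and triggers an early end-of-treatment (EOT) visit, and it is expected to be far commoner on placebo. With no inclusion rule for biomarkers, the visit windows alone decide who contributes and whether the value is on or off drug. At stake is whether the trial reports an interpretable estimate for FeNO, eosinophils, PARC, eotaxin-3, IgE, periostin, IL33, sST2 and calcitonin.

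**Working it through.** **1. Inputs.** SAP 1.3 and Protocol 11.1 give LOAC rates of 40% and 14% and 60 patients per arm. Neither document gives a figure for the biomarker analysis. The sample size behind these rates reproduces: exact power of Fisher's or the continuity-corrected test at 50 per arm is 80.0%, and 50/0.85 = 58.8, against 60 stated. Expected LOAC-free patients are 60 × 0.60 = 36 on placebo and 60 × 0.86 = 51.6 on SAR440340.

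**2. The list in Protocol 5.3 against its planned analyses.**

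| Item | Analysis | Between-arm estimate and CI |
|---|---|---|
| Other spirometry | MMRM, SAP 2.4.4.4.1 | Yes |
| Patient-reported outcomes | MMRM, Protocol 11.4.5, SAP 2.4.4.4.1 | Yes |
| Immunogenicity | Counts, SAP 2.4.7.1 | No |
| PK | Descriptive, SAP 2.4.6.1 | No |
| Biomarkers | Descriptive, SAP 2.4.6.2 | No |

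**3. Timing.** LABA stops at Week 4. ICS steps down from Week 6 and reaches zero at Week 8 or 9 (SAP Table 1). Write W for the common withdrawal effect and D for the drug effect. Late change is W on placebo and W + D on active, so only the difference isolates D. Week 2 (FeNO, eosinophils) and Week 4 (all markers) are sampled before withdrawal takes effect.

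**4. Which LOAC patients reach Week 12 (SAP Table 9).** Assume EOT falls on the LOAC day d and Visit 15 follows 141 − 85 = 56 days later.

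- FeNO, eosinophils, IL33, sST2 and calcitonin have a Week 12 window of Days 71–112.
  - d = 15–56: Visit 15 falls on Days 71–112, so an off-IMP value with ICS/LABA resumed enters Week 12.
  - d = 71 or later: the EOT value enters Week 12.
  - d = 57–70: Visit 15 falls on Days 113–126, so Week 12 is empty.
  - d = 2–14: Visit 15 falls on Days 58–70 and Visit 17 on Days 142–154, so Week 12 is also empty.
- PARC and eotaxin-3 are not sampled after EOT, so EOT before Day 71 leaves Week 12 empty.
- IgE and periostin are likewise not sampled after EOT, so EOT before Day 57 leaves Week 12 empty.

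**5. If LOAC patients are simply absent.** Let ρ be the assumed correlation between the marker and LOAC liability. The mean of those retained shifts by ρ·φ(z)/(1 − p), which is 0.644ρ at p = 0.40 and 0.259ρ at p = 0.14. For a marker that the drug lowers, the gap shrinks by 0.385ρ SD: 0, 0.12, 0.19 and 0.27 at ρ = 0, 0.3, 0.5 and 0.7. At the prior-study rates (44% v 6%) the factor is 0.58ρ, and at 40% v 30% it is 0.15ρ. For scale, the 95% CI half-width at 36 v 51.6 patients is 1.96·√(1/36 + 1/51.6) = 0.43 SD.

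**6. If post-LOAC values enter.** Assume a true gap of −0.50 SD, all LOAC patients contributing, and a common post-LOAC mean m measured from the LOAC-free placebo mean. The gap is (0.86 × −0.50 + 0.14m) − 0.40m = −0.43 − 0.26m. This gives −0.30 at m = −0.5, −0.43 at m = 0, −0.495 at m = 0.25 and −0.56 at m = 0.5. The gap can therefore shrink or widen.

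**7. What a likelihood model repairs.** Simulation with a true gap of −0.50 SD, between-visit correlation 0.6 and LOAC patients absent at Week 12:

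| LOAC depends on | Observed-case gap, ρ = 0.3 / 0.5 / 0.7 | MMRM-type gap |
|---|---|---|
| Previous observed value | −0.43 / −0.38 / −0.34 | About −0.50 each |
| Unseen concurrent value | −0.38 / −0.32 / −0.23 | −0.43 / −0.39 / −0.32 |

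**8. Precision.** The SE of a baseline-adjusted difference relative to raw change is √((1 + r)/2), where r is the baseline correlation. This is 0.95 at r = 0.8 and 0.87 at r = 0.5, a gain of 5% to 13%.

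**The case against.** The strongest defence is that this is an objective of the lowest tier in a Phase 2a trial. The same opening phrase also covers PK and immunogenicity, which are summarised descriptively too, so it does not promise a modelled contrast for every item. Placebo is tabulated beside the active arms with N, means, SD and SEM, so a crude difference and interval can be formed by hand, and the early visits give FeNO and eosinophils a contrast before withdrawal. All of this stands. It limits the seriousness, but it does not supply a prespecified, baseline-adjusted estimate, nor say which samples belong at Week 12.

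A reader might go further and infer that LOAC dropout shrinks the visible arm gap, so that the planned tables are biased toward no effect by a calculable share. The documents do not support that. They give no association between any marker and LOAC, and at zero association nothing shrinks. Nor are the late means restricted to patients who stayed in control: every early-discontinuing patient is to have an EOT visit with biomarker sampling, no exclusion rule covers these values, and Table 9 places many of them, or later off-drug samples, in Week 12.

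**Conclusion.** The mismatch holds on the text alone: a comparative objective, a purely descriptive analysis, and no biomarker in Table 4, Table 5 or the MMRM list. So does the point about withdrawal, confined to Weeks 8 and 12. It would be too strong to say that the drug effect can never be estimated; what is missing is a prespecified estimate.

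Distortion of the Week 12 contrast is possible, but its size and sign are undetermined. Under the stated assumptions it runs from nothing to 0.27 SD of shrinkage through absence (at ρ up to 0.7), and it can go either way when post-LOAC values enter. The SAP's account of amendment 1 (section 1.5) itself accepts that EOT data after LOAC could confound the treatment effect, yet the resulting rule stops at the efficacy endpoints. This is worth correcting, but it does not touch the primary or secondary analyses.

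**What to change.** In SAP 2.4.6.2 add, for each biomarker, the MMRM already specified for other continuous endpoints, fitted to log values: treatment, eosinophil strata, region, ICS dose level, visit, treatment-by-visit, log baseline and baseline-by-visit. Report ratios of geometric means with 95% CIs for the five Table 4 comparisons at each scheduled visit up to Week 12.

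State the data rule alongside it. Apply the Table 5 inclusion rules to biomarker values in this model, and exclude follow-up samples taken after EOT from the Week 12 window. Without that rule the model would take in the off-drug values that Table 9 maps to Week 12. Report Week 4 as the contrast before ICS withdrawal where it was collected. Label any p-values nominal and keep the descriptive tables as support.

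The cost is SAP wording and some extra analysis work on existing code, with no new data. The inclusion rule makes more Week 12 values missing, so the report should say that the estimate is free of LOAC-selection bias only under missing at random.

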### **11.4.5 Analyses of patient reported outcomes (health-related quality of life/health economics variables)**

Change from baseline in the following variables: global measure and the 4 domains of AQLQ and RQLQ will be analyzed using an MMRM approach, described previously for the continuous efficacy variables. Descriptive statistics including number of patients, mean, standard error, and LS means will be provided. In addition, the difference in LS means, the corresponding 95% CIs, and the p-values will be provided.

## **11.5 INTERIM ANALYSIS**

No formal interim analysis is planned. Analyses will be performed for safety monitoring and internal decision making. No formal stopping rules or adjustment for multiplicity will be applied.

## 12 ETHICAL AND REGULATORY CONSIDERATIONS

### 12.1 ETHICAL AND REGULATORY STANDARDS

This clinical trial will be conducted by the Sponsor, the Investigator, and delegated Investigator staff and Subinvestigator, in accordance with consensus ethics principles derived from international ethics guidelines, including the Declaration of Helsinki, and the International Conference on Harmonisation (ICH) guidelines for good clinical practice (GCP), all applicable laws, rules and regulations.

This clinical trial will be recorded in a free, publicly accessible, internet-based registry, no later than 21 days after the first patient enrollment, in compliance with applicable regulatory requirements and with Sanofi public disclosure commitments.

### 12.2 INFORMED CONSENT

The Investigator (according to applicable regulatory requirements), or a person designated by the Investigator, and under the Investigator's responsibility, should fully inform the patient of all pertinent aspects of the clinical trial including the written information giving approval/favorable opinion by the ethics committee (IRB/IEC). All participants should be informed to the fullest extent possible about the study, in language and terms they are able to understand.

Prior to a patient's participation in the clinical trial, the written ICF should be signed, name filled in and personally dated by the patient or by the patient's legally acceptable representative, and by the person who conducted the informed consent discussion. A copy of the signed and dated written ICF will be provided to the patient.

If informed consent is obtained under special circumstances (emergency, etc), the method should be specified following the ICH requirements.

Prior to collection of blood for pharmacogenetics, the optional pharmacogenetic section of ICF (written) should be completed by the patient or by the subject's legally acceptable representative, and by the person who conducted the informed consent discussion.

The ICF, including the optional pharmacogenetic sample and optional future use of samples, used by the Investigator for obtaining the patient's informed consent must be reviewed and approved by the Sponsor prior to submission to the appropriate ethics committee (IRB/IEC) for approval/favorable opinion.

### **12.3 HEALTH AUTHORITIES AND INSTITUTIONAL REVIEW BOARD/INDEPENDENT ETHICS COMMITTEE (IRB/IEC)**

As required by local regulation, the Investigator or the Sponsor must submit this clinical trial protocol to the health authorities (competent regulatory authority) and the appropriate IRB/IEC, and is required to forward to the respective other party a copy of the written and dated approval/favorable opinion signed by the chairman with IRB/IEC composition.

The clinical trial (study number, clinical trial protocol title, and version number), the documents reviewed (clinical trial protocol, ICF, IB with any addenda or labeling documents [summary of product characteristics, package insert], Investigator's curriculum vitae [CV], etc) and the date of the review should be clearly stated on the written (IRB/IEC) approval/favorable opinion.

The IMP will not be released at the study site and the Investigator will not start the study before the written and dated approval/favorable opinion is received by the Investigator and the Sponsor.

During the clinical trial, any amendment or modification to the clinical trial protocol should be submitted to the health authorities (competent regulatory authority), as required by local regulation, in addition to the IRB/IEC before implementation, unless the change is necessary to eliminate an immediate hazard to the patients, in which case the health authorities (competent regulatory authority) and the IRB/IEC should be informed as soon as possible. They should also be informed of any event likely to affect the safety of patients or the continued conduct of the clinical trial, in particular any change in safety. All updates to the IB or labeling information will be sent to the IRB/IEC and to health authorities (competent regulatory authority), as required by local regulation.

A progress report is sent to the IRB/IEC at least annually and a summary of the clinical trial's outcome at the end of the clinical trial.

